4 INVESTIGATIONAL PLAN

4.1 Study Design

This is a single-center, prospective, open label, feasibility study in healthy adult participants. Eligible participants who have signed an informed consent will be enrolled in the study. The participant will be assigned a unique ID number. After obtaining relevant demographic information, testing will ensue.

Baseline vital sign measurement (heart rate, temperature, blood pressure, respiratory rate) will be obtained. The participant will then undergo continuous MRI of the brain to include sequences that enable thermography. Baseline imaging sequences will take approximately 30 minutes. The investigator or designee will turn on the VCool System, while the VCool remains outside of the MRI suite, for up to two hours or until the target temperature of 35.5°C is reached. Body temperature will be continuously measured using a MRI compatible thermometer. During the cooling period and once endpoint is reached the participant will undergo repeated MRI with thermography. Once study endpoint is reached, the participant will be taken off of VCool and MRI thermography. If the target core body temperature is reached before 2 hours, the participant will be monitored until two hours are completed to determine if the VCool System can maintain the participant's core body temperature between 35°C and 36°C for one hour.

During the study, the participants will have their temperature monitored and will be assessed for shivering and adverse events.

Study participation is one visit lasting approximately 4 hours.

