7.6 Procedure

7.6.1 **VCool System Set Up**

Attach the disposable delivery tube to the VCool System

Install the gas inlet filter on the back with the filter bowl vertical (glass side down)

Attach the air hose to the gas inlet filter

Connect the power cord to a grounded outlet

Turn the power switch to "ON"

Connect the RS232 cable to the VCool System and to the laptop computer

Turn on the computer

Select the following:

TC-48-20 program.

COM5

Communications

Set Point and set value to -19.0

Controller options

Save data to file

Go to file Explorer, select LabView Data

Select New and enter participant identification number as file name

Save data to file

Turn on gas and set flow meter to 35 liters per minute.

Confirm temperature is set to -10°C

Confirm gas temperature setting at the end of the delivery tube is -5°C

Attach nasal cannula to the delivery tube

7.6.2 *MR Imaging procedure*

- Participants will undergo MRI at the HSF3 research facility at the University of Maryland, Baltimore (UIMB). Each imaging session will last approximately 90 minutes. The protocol will include high-resolution anatomical MRI for structural reference and tissue segmentation; MR Spectroscopy (MRS) to measure metabolite and water resonance frequencies for temperature estimation; MR Thermometry to measure phase changes over time to track temperature dynamics; Perfusion MRI to measure cerebral blood flow (CBF); as well as other structural and functional imaging sequences. These sequences will be repeated at multiple time points during the controlled cooling period to monitor temporal changes in temperature, perfusion, and tissue properties.

7.6.3 *Participant Set Up and Monitoring*

Have the participant lie on their back in an inclined position and place the nasal cannula on the participant, securing the straps around their head

Record the temperature from both temperature sensors and record the time

Record the flow rate

Initiate the cooling and record the time. The induction phase for participant cooling can take up to 2 hours.

Record the core body temperature every 2 minutes from both temperature sensors and record the time. The core body temperature is monitored throughout the study.

If the core body temperature is <35°C for 5 minutes:

1. Remove nasal cannula, if temperature starts to rise after 2 minutes keep cannula off until temperature gets back to 35°C. Then reapply nasal cannula and resume treatment.

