2. If temperature continues to fall below 35°C after 2 minutes, cover patient with electric blanket that has been pre heated on standby. Keep blanket on until temperature gets back to 35°C.

Assess for shivering every 10 minutes using the BSAS. Record the results and time. The BSAS is recorded throughout the study.

Bedside Shivering Assessment Scale

0	None
1	Mild: Shivering localized to neck/thorax
2	Moderate: Intermittent involvement of the upper extremities and/or thorax
3	Severe: Generalized shivering or sustained upper and/or lower extremity shivering

The flow can be increased to 40 liters per minute after 10 minutes

Record any VCool System adjustments to flow rate or temperature and record the new flow rate and temperature and time of adjustment. Record the reason for the adjustment.

Assess the participant for adverse events (AEs) throughout the study

If the participant has a nosebleed, discontinue the study and note the time.

Monitor patient at first sign of shivering

- If **Mild**, cover patient with regular blanket.
- If **Moderate or severe** – discontinue cooling treatment.

Continue to record the temperature until either temperature sensor reaches 35.5°C or the VCool System has been used for 2 hours. Note the time the target temperature was achieved.

If the participant's core body temperature does not reach 35.5°C in 2 hours, the study is concluded

- Remove the nasal cannula from the participant and dispose of it properly
- Monitor the participant's core body temperature until it returns to baseline. Blankets can be applied to help with warming.
- Remove the axillary thermometer

If the participant's core body temperature reaches 35.5°C, proceed to the next steps

Maintain the target temperature of 35.0°C to 36.0°C for 1 hour:

Adjust flow rate by 5 liters per minute from baseline every 2 minutes

- If temperature falls below 35°C., reduce flow rate by 5 liters per minute every 2 minutes until temperature rises back to 35°C
- If temperature rises above 36°C, increase flowrate 5 liters per minute every 2 minutes until temp falls below 36°C

Remove the nasal cannula and the air delivery tube and dispose of them properly

Once out of the MRI suite, record the patient temperature (°C) using the 3M SpotOn® zero-heat-flux forehead sensor, the Braun ThermoScan 7 tympanic sensor

Monitor the participant's core body temperature until it returns to baseline. Blankets can be applied to help with warming.

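### The second step of the below-35°C rescue (Protocol 7.6.3) calls for an electric blanket when the participant may still be in the MRI suite, with no location or MRI-safety condition

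*Protocol*

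**What the plan says.** Section 7.6.3 of the Protocol triggers a rescue when core temperature has been below 35°C for 5 minutes.

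- Step 1: "Remove nasal cannula, if temperature starts to rise after 2 minutes", leave it off until 35°C is regained, then put it back and continue treatment.
- Step 2: if the temperature is still falling after those 2 minutes, "cover patient with electric blanket that has been pre heated on standby", and keep it on until 35°C is regained.

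Neither step names a place, asks for the scan to stop, or sets an MRI condition for the blanket.

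On where the participant is, section 4.1 describes continuous brain MRI and adds: "During the cooling period and once endpoint is reached the participant will undergo repeated MRI with thermography". In section 7.6.3 the first sign that the participant has left comes after the maintenance hour and cannula removal: "Once out of the MRI suite, record the patient temperature".

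Other equipment does have MRI controls. Section 4.1 keeps the VCool out of the suite and states: "Body temperature will be continuously measured using a MRI compatible thermometer". Section 7.5 has the forehead and tympanic sensors taken off before the participant goes in.

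**The concern.** An electric blanket is not an item that staff can assume is safe near a scanner, and the protocol treats MRI suitability as something it should specify for other items. If the rescue is needed while the participant is in the suite, the text as written leaves two poor options. Staff may bring in an electric item that nobody has stated to be MRI safe, or they may find that the last rewarming step cannot be used there while temperature is still falling.

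These are healthy volunteers who gain no direct benefit, and section 2.3.1 lists overcooling as a risk. The blanket is the only active warming named in the below-35°C rescue. The mitigation in section 2.3.2 speaks only of adjusting the VCool, so it does not close the gap.

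**Working it through.** This is a check of texts against each other. The plan gives no figure to reproduce, and the only arithmetic is the timing of the step.

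**1. When step 2 can be reached.** Inputs from section 7.6.3: target 35.5°C, rescue threshold 35°C, 5 minutes below threshold, then 2 minutes with the cannula off.

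- Further fall needed after target: 35.5 − 35.0 = 0.5°C, and then below that.
- Earliest time for the blanket: 5 + 2 = 7 minutes after crossing 35°C.
- In the maintenance hour a separate rule acts first: "reduce flow rate by 5 liters per minute every 2 minutes until temperature rises back to 35°C". Step 2 therefore also requires that this rule has not reversed the fall.

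On the normal path the step thus falls after 35.5°C is reached, so in practice in the maintenance period.

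**2. Where the participant is at that time.**

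Pointing to the MRI suite:
- Section 4.1 continues repeated MRI once the endpoint is reached, not only during cooling.
- Section 7.6.3 lists leaving the suite only after maintenance and cannula removal. The two sensors removed before entry are used again only then.
- Step 1 expects the cannula to be put back and treatment to go on. That describes a pause within a session and mentions no exit.

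Pointing elsewhere:
- Section 4.1 also says: "Once study endpoint is reached, the participant will be taken off of VCool and MRI thermography". If that endpoint is 35.5°C, a later fall below 35°C could occur outside the scanner.
- Section 7.6.2 says: "These sequences will be repeated at multiple time points during the controlled cooling period", which need not include maintenance. It gives a session of about 90 minutes. If the 30 minutes of baseline imaging in section 4.1 count within it (an assumption), 90 − 30 = 60 minutes remain, against up to 2 hours of induction plus 1 hour of maintenance.
- The list in section 7.6.3 is not in clean order. An instruction to remove sensors before going to the suite appears after the step for having left it.

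Presence in the suite is the more natural reading, but it remains an inference.

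**3. What controls exist for each item.**

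| Item | MRI control in the Protocol |
|---|---|
| VCool unit | Kept out of the suite (4.1) |
| Forehead and tympanic sensors | Removed before entry (7.5) |
| Thermometer used during the session | MRI compatible (4.1); the axillary sensor is so described (7.5) |
| Electric blanket | None |

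The other mentions of blankets in section 7.6.3, an ordinary one for mild shivering and optional ones for rewarming at the end, do not address the point.

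**The case against.** The strongest reply is that this is silence and not a wrong statement. The text never says that the blanket enters the scanner room, is used during a scan, or is under power when applied, and a blanket on standby could be waiting outside. Location is uncertain for the reasons set out above, and the deeper problem may be the unclear timing of MRI relative to the maintenance hour. The harm needs several things together: a fall below 35°C despite flow reduction, 5 minutes there, a continuing fall after cannula removal, a participant still in the suite, and staff at an MRI research facility bringing in an unsuitable item. Staff training (section 17) and the Investigator's freedom to discontinue a participant (section 8) lower the risk further.

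Much of this stands. It limits the claim to a participant who may be in the suite, and it keeps the probability low. It does not supply the missing instruction: neither section 17 nor section 8 mentions the blanket or leaving the suite, and the protocol cites no facility MRI rules. If the participant could be in either place when step 2 applies, that is itself a reason to state the place.

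A reader might infer more, namely that the protocol directs staff to use a powered blanket in the scanner. The documents do not support that, because step 2 gives no place and does not say that the blanket is connected when applied.

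**Conclusion.** The point holds as a small participant-safety correction. The rescue rule names an electric item at a stage when the participant may still be in the MRI suite, and this item lacks the kind of MRI control that the protocol gives to the other equipment. Followed literally in the suite, the rule is either unsafe or unusable.

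No frequency can be given from the document. The step is conditional and probably rare, and its earliest occurrence is about 7 minutes after crossing 35°C. The conclusion assumes that MRI may continue into the maintenance hour, which section 4.1 supports but does not settle. It would also be tempting to see a threat to the results; the gap changes no endpoint definition and no analysis.

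**What to change.** Amend the rescue in section 7.6.3 in one of two ways.

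- **Move out early.** At step 1, when the cannula comes off after 5 minutes below 35°C, stop the scan and start moving the participant out of the MRI suite. Keep the electric blanket on standby outside, so that it can be applied at 2 minutes if temperature is still falling.
- **Warm inside.** Specify an MRI-safe method for use in the suite, for example pre-warmed non-electric blankets.

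Either is a clause or two of text. The first loses later thermography in that participant, including in some whose temperature would have recovered after step 1 alone. Starting the move only at step 2 would spare those scans but would delay active rewarming for a short time while temperature is falling, so step 1 is the better trigger. The second keeps the participant in place but needs a suitable item at hand.

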5.2 Secondary Endpoint

4. To assess the shivering experienced by participants based on the 4-point Bedside Shivering Assessment Scale (BSAS).

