12.2 Secondary Analysis

The incidence of any shivering will be analyzed using the BSAS. The incidence and nature of any adverse events or participant intolerance will be tabulated.

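### The shivering scale printed in Protocol 7.6.3 puts intermittent thorax-only shivering in two grades and intermittent leg-only shivering in none, and the overlap falls on the line between a blanket and stopping cooling.

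*Protocol*

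**What the plan says.** Section 7.6.3 of the Protocol prints the scale that staff apply at the bedside. Besides 0 for none, it has three grades:

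- Grade 1: "Mild: Shivering localized to neck/thorax"
- Grade 2: "Moderate: Intermittent involvement of the upper extremities and/or thorax"
- Grade 3: "Severe: Generalized shivering or sustained upper and/or lower extremity shivering"

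Grading is frequent: "Assess for shivering every 10 minutes using the BSAS". Staff record the result and the time; body regions are not asked for.

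The same section links grade to action. For mild shivering the instruction is to "cover patient with regular blanket". For moderate or severe it is to "discontinue cooling treatment".

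The scale is also the basis of the only secondary endpoint (section 5.2). Section 12.2 states the analysis: "The incidence of any shivering will be analyzed using the BSAS". Section 2.3.2 (Risk Mitigation) gives another BSAS-based rule: device flow and temperature are adjusted when shivering is severe. It names no action for moderate shivering.

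**The concern.** An ordinal scale that triggers an action should give each observation one grade and leave none without a grade. The printed table fails on both counts, and the double-graded pattern lies on the boundary where, under 7.6.3, the instruction changes from a blanket to stopping cooling. The pattern with no grade has no assigned action.

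Three results could be touched:

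- the number of participants who reach 35.5°C within 2 hours (section 12.1), if cooling is stopped during induction;
- the maintenance endpoint (section 5.1), if cooling is stopped later;
- any description of shivering by grade.

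An analysis plan cannot repair this afterwards. The grade is applied in real time, and the data needed to regrade (which regions, intermittent or sustained) are not collected.

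**Working it through.** There is no stated figure to reproduce. The check is to cross each single body site with duration and match it to the printed wording.

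**Inputs (all 7.6.3).** Grade 1: neck or thorax, no duration given. Grade 2: intermittent; upper extremities, thorax, or both. Grade 3: generalized, or sustained in upper or lower extremities.

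| Site | Intermittent | Sustained |
|---|---|---|
| Neck only | 1 | 1 |
| Thorax only | **1 and 2** | 1 |
| Upper extremities only | 2 | 3 |
| Lower extremities only | **no grade** | 3 |

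Of 4 × 2 = 8 patterns, 6 fit exactly one grade, 1 fits two and 1 fits none (6 + 1 + 1 = 8). Generalized shivering is grade 3. Patterns combining sites short of generalized were not enumerated.

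**Does an obvious convention resolve it?**

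- Take the higher matching grade: intermittent thoracic shivering becomes grade 2 while sustained thoracic shivering stays at grade 1, so the scale ranks intermittent above sustained.
- Treat thorax alone as always grade 1: the 'or' before thorax in grade 2 then has no effect.
- Neither convention gives intermittent leg-only shivering a grade.

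No other section defines the grades or gives a tie-break.

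**Actions side by side.**

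| BSAS grade | Section 7.6.3 | Section 2.3.2 |
|---|---|---|
| Mild | regular blanket | none named |
| Moderate | cooling stopped | none named |
| Severe | cooling stopped | flow and temperature adjusted |

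Under 7.6.3 the line between grades 1 and 2 decides whether cooling is stopped. Under 2.3.2 it triggers nothing. The two sections conflict at severe and differ at moderate.

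**Effect on the reach count.** Section 4.3 plans 10 completers, so one participant is 1/10 = 10 percentage points. A grade of 2 rather than 1 changes the count only if all of these hold: the shivering is intermittent and confined to the thorax; it occurs before 35.5°C is reached; and the participant would otherwise have reached 35.5°C within 2 hours. Hence at most 1 of 10 per such participant.

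**Effect on the secondary analysis.** Grades 1 and 2 both count as shivering, so the overlap leaves the incidence of any shivering unchanged. It moves participants between grades in a summary by grade. The leg gap could lower the incidence only if an ungraded observation were entered as 0.

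**The case against.** The case for leaving this alone is that it is a narrow wording problem in a 10-participant, open-label feasibility study with descriptive counts. Staff are to be trained on study procedures (section 17), and shivering is a listed anticipated adverse event (section 11), so leg shivering has a second route of capture. The overlap might also belong to the instrument itself, in which case rewriting the grades would create a modified scale. These points limit the size and shape the remedy. They do not remove the fault, because trained staff would still be working from a table that permits two grades with different actions.

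A reader might infer more than the documents support:

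- *That all thorax-only shivering is double-graded.* Only the intermittent form is; sustained thoracic shivering fits grade 1 alone.
- *That the secondary endpoint result changes.* The analysis named in 12.2 does not change with a grade of 1 rather than 2.
- *That the reach rate could move by several participants.* The documents give no frequency for this pattern, so any such range would be a guessed number divided by 10.
- *That repeated grading multiplies the effect.* A full induction has 120/10 = 12 gradings, but the result is one yes or no per participant. Gradings in the maintenance hour cannot affect the reach count, because the target has already been reached.
- *That the table misprints the published scale.* The source is not in the documents, so this cannot be judged.

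**Conclusion.** The point holds in limited form. As printed, the BSAS table is neither mutually exclusive nor exhaustive: one of eight single-site patterns has two grades and one has none. Under 7.6.3 the double grade can lead to opposite actions on the same observation. The effect on the reach count is bounded at 1 of 10 for each participant who meets the conditions above; how many would do so is unknown. A later stop bears on the maintenance endpoint instead.

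This rests on three readings: 'and/or' admits thorax alone; cooling continues at grade 1, which is implied because only a blanket is ordered; and a participant stopped for shivering stays among the ten. It also takes 7.6.3 as the operative action rule, which the conflict with 2.3.2 leaves open. The table should be corrected before use, mainly because it costs little and cannot be repaired from the data afterwards.

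**What to change.** 1. Check the table in 7.6.3 against the source version of the instrument. If the overlap and gap are transcription slips, reword the table. If they belong to the instrument, keep its wording and add a short scoring convention to the Protocol and case report form. Either way, each pattern should fall in exactly one grade.
2. At each assessment, record the body regions involved and whether the shivering is intermittent or sustained, so that grades can be verified. State that shivering which fits no printed grade is not to be entered as 0.
3. Reconcile 2.3.2 with 7.6.3 on the action for moderate and severe shivering, and have the sponsor confirm which action attaches to each grade once the grades are settled. Placing leg shivering or thoracic shivering in a grade also fixes its action, so that decision belongs to the sponsor and the investigator. No clinical rule is proposed here.

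The cost is the wording of one table or one convention, a small addition to the case report form, one reconciled sentence, and coverage in the training already planned. No extra assessments or participants are needed.

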5 STUDY ENDPOINTS

5.1 Primary Endpoints

1. To confirm the VCool System can lower core body temperature to 35.5°C within 2 hours.
2. To identify whether cooling with the VCool System results in a gradient between brain and core body temperature.
3. To confirm the VCool System can maintain a core body temperature between 35°C and 36°C for one hour after cooling.

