12 DATA ANALYSIS

12.1 Primary Analysis

The time and flow rate that is required to reduce and maintain each participant's core temperature to 35.5°C from measured baseline temperature will be calculated. The total number of participants who reach the target temperature in 2 hours or less will be calculated.

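### Section 7.6.3 does not require times for cannula removals or blankets, so delivered flow and unassisted temperature control cannot be read accurately from the record

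*Protocol*

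**What the plan says.** All three actions are in Protocol section 7.6.3.

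- **Cannula.** When core temperature has been under 35°C for 5 minutes: "Remove nasal cannula, if temperature starts to rise after 2 minutes keep cannula off until temperature gets back to 35°C". The next sentence is "Then reapply nasal cannula and resume treatment", so the participant stays in the study phase being measured.
- **Electric blanket.** If the fall continues after 2 minutes: "cover patient with electric blanket that has been pre heated on standby. Keep blanket on until temperature gets back to 35°C".
- **Regular blanket.** For mild shivering: "cover patient with regular blanket". Only moderate or severe shivering ends cooling, so here cooling goes on under the blanket.

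The recording line for changes is "Record any VCool System adjustments to flow rate or temperature and record the new flow rate and temperature and time of adjustment"; the sentence after it adds the reason. Cannula removal and blankets are not in it.

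On the analysis side, section 5.1 attributes induction to the device ("To confirm the VCool System can lower core body temperature to 35.5°C within 2 hours") and does the same for staying between 35°C and 36°C for an hour. Section 12.1 begins "The time and flow rate that is required to reduce and maintain" and mentions neither blankets nor cannula-off time. Section 2.2 wants the data for a control algorithm, with cooling response modelled on flow rate and on how long air is supplied.

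**The concern.** Section 7.6.3 is detailed about what to write down and when. It asks for times for the start of cooling, the 2-minute temperatures, the shivering scores, reaching the target, a nosebleed, and changes to device settings. Against that list, the absence of the cannula and the blankets stands out.

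Two quantities are at stake. One is delivered flow: taking the cannula off stops air reaching the nose without altering the flow-meter setting, so a record of settings shows flow that the participant did not receive. The other is attribution: a participant who returned to range with external heat, or who cooled under a blanket, looks in the data like one managed by VCool alone. An analysis plan can set a rule for such periods, but it cannot fully supply times that nobody recorded.

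**Working it through.** The protocol gives no figure for this point, so there is none to reproduce. The check sets each action against the recording rules and then illustrates the size.

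**Step 1. Which phase each action can touch.** Induction ends when either sensor reads 35.5°C (7.6.3), and entry requires at least 36.8°C (6.1). A participant therefore cannot spend 5 minutes under 35°C before induction has ended.

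| Action | Phase affected | On/off times required? | Nearest indirect trace |
|---|---|---|---|
| Cannula off and on | Essentially the maintenance hour | No | 2-minute temperatures |
| Electric blanket | Essentially the maintenance hour | No | 2-minute temperatures |
| Regular blanket | Induction and maintenance | No | 10-minute shivering scores; none for removal |

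**Step 2. Readings while a low-temperature step is active.** Both steps end when 35°C is regained. (The reapplication sentence is written in the first branch; I read it as applying to both.) Readings during these steps are therefore below 35°C, apart from the one that ends the step, and are already outside the 35–36°C band. What remains open is the participant-level result: the protocol does not say whether such an excursion fails the maintenance endpoint, and treatment resumes afterwards.

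**Step 3. Delivered against recorded flow.** Inputs: set flow 35 L/min (7.6.1), a 60-minute maintenance phase (5.1, 7.6.3), and cannula-off time t, which is an assumption.

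Mean delivered flow = 35 × (60 − t)/60. Overstatement = 60/(60 − t) − 1.

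| t (min) | Delivered (L/min) | Overstatement |
|---|---|---|
| 2 | 33.8 | 3.4% |
| 5 | 32.1 | 9.1% |
| 10 | 29.2 | 20.0% |
| 20 | 23.3 | 50.0% |

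The percentages are the same at 40 L/min.

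**Step 4. Allowing for logged flow cuts.** In the maintenance hour, 7.6.3 also lowers flow by 5 L/min every 2 minutes below 35°C. If two cuts are logged before removal, the recorded setting while the cannula is off is 35 − 10 = 25 L/min. Taking 35 L/min for the rest of the hour, for simplicity, overstatement = 25t/[35 × (60 − t)]:

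- t = 2: 50/2030 = 2.5%
- t = 5: 125/1925 = 6.5%
- t = 10: 250/1750 = 14.3%
- t = 20: 500/1400 = 35.7%

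The distortion is smaller but does not vanish.

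**Step 5. Weight of one participant.** With 10 completers, reclassifying one moves a success proportion by 1/10, or 10 percentage points. For example, 9/10 (exact 95% interval 55.5–99.7%) becomes 8/10 (44.4–97.5%).

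**The case against.** The strongest reply is that the protocol's own stopping rules limit the harm and leave traces. Most of it stands.

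- **In-range readings.** A reader might infer that readings brought back into 35–36°C by a heated blanket, with the cannula off, are themselves counted as maintained. The documents do not support this: both steps end at 35°C, so those readings are out of band. Only the assisted return and the participant-level result remain in question. If an excursion does fail the endpoint, there is no false success, but the flow data are still affected.
- **Endpoint 1.** A reader might infer that cannula removal and the electric blanket distort time to 35.5°C. They cannot in practice, since induction has ended by then. Only the regular blanket can, and the documents give neither the direction nor the size of its effect.
- **Reconstruction.** Cannula and electric-blanket times follow temperature thresholds and could be roughly rebuilt from the 2-minute readings if the steps were followed exactly. The start of a regular blanket can be bracketed by the shivering scores. Its removal has no trace, and actual cannula-off time remains an inference.
- **Other records.** The adverse event form has a field for action taken (10.1), section 13 requires adequate records, and section 2.3.2 describes the response below 35°C as adjusting the VCool. None of these requires on and off times, and no reading makes a blanket a device adjustment. The CRF is not shown and might capture some of this.
- **Size.** Every duration used above is assumed, and the number of participants affected could be zero.

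**Conclusion.** The point holds as a gap in data capture. Section 7.6.3 orders three actions that change heat balance during the measured phases and requires times for none of them. Followed as written, the flow record can show the set value while delivered flow is zero, which affects the flow rate in 12.1 and the response data in 2.2. Blanket-assisted results cannot be reliably told apart from unassisted ones.

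The size depends on unknown frequency and duration. With 2 to 20 minutes off, mean flow over the hour is overstated by 3.4% to 50% at a constant setting, or by 2.5% to 35.7% if two flow cuts were already logged. Each participant reclassified is 10 percentage points.

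The documents support saying that warming and pauses can be credited to or blamed on VCool, not that they will be. The change should be made because it costs little and the missing times cannot be fully recovered later.

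**What to change.** 1. Extend the recording line in 7.6.3, and the CRF, to the start time, stop time and reason for each cannula removal and for each regular or electric blanket used in the induction and maintenance phases.
2. In 12.1, treat delivered flow as zero while the cannula is off.
3. In 12.1, flag participants whose induction or maintenance result was blanket-assisted or interrupted, and report the counts with and without them.
4. Reconcile the two responses to a temperature below 35°C in 7.6.3: cannula removal under monitoring, and stepwise flow reduction in the maintenance steps. As written, it is unclear which flow record to expect during an excursion.

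The cost is a few CRF time fields and a sentence or two in 12.1. The maintenance figure may look slightly less favourable. No change is proposed to when blankets or cannula removal are used.
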